10.7. Study Stopping Rules

The Sponsor has the right to terminate the study prematurely for safety reasons. In addition, the Sponsor may terminate the study prematurely for administrative reasons at any time. In all cases all necessary measures have to be taken to guarantee appropriate safety follow-up of all patients already included in the study.

The IEC or IRB and the Regulatory Authorities will be informed in writing about any premature termination of the study.

CELGENE PROPRIETARY INFORMATION

11. METHODS OF ASSESSMENT

Tests and assessments are common to Parts A and B of the study unless otherwise indicated.

The study design is shown in [Figure 1](#). Tests and Assessments are outlined [Table 1](#) and [Table 2](#) (Part A), [Table 3](#) and [Table 4](#) (Part B), and [Table 5](#) (cardiac monitoring during dose titration), and additional detail regarding procedure is included in [Section 10](#).

11.1. Efficacy Assessments

11.1.1. Magnetic Resonance Imaging (MRI)

Brain MRIs will be acquired with and without Gadolinium. The same MRI protocol will be used across all sites. To ensure quality data and standardization the same machine and software should be used throughout the study. MRIs for MS lesions will be read blinded to treatment allocation at a centralized reading facility.

In Part B and in the Blinded Extension to Part A, MRI scans should not be performed until 30 days after the last dose of methylprednisolone treatment for relapse. Previously scheduled MRIs should be rescheduled as necessary if a relapse occurs.

Total number of GdE lesions, number of new or enlarging hyperintense T2-weighted lesions, lesion volume (T2-weighted images), volume of unenhancing T1-weighted lesions and brain volume (i.e., brain atrophy) will be collected and reported.

The MRI scans will be read locally for non-MS pathology.

11.1.2. Expanded Disability Status Scale (EDSS) and Neurological Examination

The EDSS is a standardized method, widely accepted, numerical scale used to evaluate disability in people with MS ([Kurtzke, 1983](#)).

The EDSS is evaluated according to signs and symptoms observed during a standard neurological examination. These clinical observations are classified in 7 FS scales, each of them grading signs and symptoms for different neurological functions: pyramidal, cerebellar, brainstem, sensory, bowel or bladder, visual, and cerebral.

The study will require the same blinded evaluator (refer to [Section 9.1.2.2](#)) should perform all EDSS assessments for an individual patient when possible. In addition, EDSS raters will be certified using the Neurostatus Standardized Examination and Assessment prior to study initiation and examiners will be re-certified every two years throughout the conduct of the study.

11.1.3. Relapse Assessment

A relapse is defined as the occurrence of new or worsening neurological symptoms attributable to MS and immediately preceded by a relatively stable or improving neurological state of at least 30 days. The new or worsening neurological symptoms must be accompanied by objective neurological worsening consistent with an increase of at least half a point on the EDSS, or 2 points on one of the appropriate FS scores, or 1 point on two or more of the appropriate FS scores. The change must be documented by the blinded evaluator at either scheduled or unscheduled visits and must affect the FS scales that correspond to the patient's symptoms (e.g.,

pyramidal, gait, cerebellar, brainstem, sensory, or visual). Symptoms must persist for > 24 hours and should not be attributable to confounding clinical factors (e.g. fever, infection, injury, adverse reactions to concomitant medications). When a patient experiences new or worsening symptoms that may indicate a possible relapse, he/she should telephone the treating investigator within 48 hours of symptoms onset. The treating investigator, study nurse, or other medically qualified individual will conduct a telephone questionnaire and, as necessary, will arrange an unscheduled relapse assessment visit.

11.1.4. Multiple Sclerosis Functional Composite (MSFC)

The MSFC (Cutter, 1999) is a battery of the following 3 individual scales:

- The Timed 25-Foot Walk is a quantitative measure of lower extremity function
- The 9-Hole Peg Test is a quantitative measure of upper extremity (arm and hand) function
- The PASAT-3 is a measure of executive function cognition that specifically assesses auditory information, processing speed, and flexibility, as well as calculation ability

The same person, either the blinded evaluator or another independent designated team member trained in conducting MSFC assessments should administer the 3 scales that make up the MSFC with each participating patient throughout the study.

The MSFC z-score is calculated by creating z-scores for each component of the MSFC, as explained below, and averaging them to create an overall composite score, i.e.,

$$\text{MSFC z-score} = (Z_{25\text{-foot-walk}} + Z_{9\text{HPT}} + Z_{\text{PASAT3}})/3, \text{ where } Z_{xxx} \text{ refers to Z-scores}$$

Details on the calculations of the z-score for each component will be described in the statistical analysis plan (SAP).

11.1.5. Low-Contrast Letter Acuity Test (LCLA)

The LCLA, which is performed with the MSFC assessments, is performed with a standardized set of charts (e.g. Sloan letter charts or Tumbling E charts) to assess low contrast visual acuity. Each chart corresponds to a different contrast level, and charts are scored according to the number of letters that are identified correctly. The LCLA captures aspects of neurological dysfunction that is not assessed by the EDSS or MSFC, and has been proposed as an additional component to the MSFC (Balcer, 2003).

11.1.6. Multiple Sclerosis Quality of Life-54 (MSQOL-54)

The MSQOL-54 is a multidimensional health-related quality of life measure that combines both generic and MS-specific items into a single instrument (Vickrey, 1995). This 54-item instrument generates 12 subscales along with two summary scores, and two additional single-item measures. The subscales are: physical function, role limitations-physical, role limitations-emotional, pain, emotional well-being, energy, health perceptions, social function, cognitive function, health distress, overall quality of life, and sexual function. The summary scores are the physical health composite summary and the mental health composite summary. The single item measures are satisfaction with sexual function and change in health.

The MSQOL-54 is a structured, self-report questionnaire that the patient can generally complete with little or no assistance. It may also be administered by an interviewer. However, patients with visual or upper extremity impairments may need to have the MSQOL-54 administered as an interview by the study nurse (or study coordinator). Interviewers should be trained in basic interviewing skills and in the use of this instrument.

11.2. Safety Assessments

11.2.1. Clinical Safety Assessments

Physical Examination

A complete physical examination will include evaluation of heart, lung, head and neck, abdominal, skin, and extremities. The EDSS, performed by the blinded evaluator, serves as the neurological examination. An interim (or brief) physical examination will include areas with previously noted abnormalities and/or that are associated with any new complaints from the patient.

Initial neurological examination will be a part of the physical examination at screening and if warranted by an unscheduled visit. All significant findings that are present at screening must be reported on the relevant medical history/current medical conditions eCRF. Significant findings made after randomization that meet the definition of an AE must be recorded on the AEs eCRF.

Height and Weight

Height will be measured at screening in Part A and Part B and at the end of the study.

Weight will be measured at screening, Baseline (Day 1), Week 24 and end of study or early termination in Part A and screening, Baseline (Day 1), Month 12, and Month 24 or early termination in Part B.

Vital Signs

Blood pressure, heart rate and body temperature will be assessed.

For the Baseline (Day 1) visit and during dose titration (Day 5 and Day 8, as applicable), vital signs should be recorded after the patient has been supine for 10-15 minutes, systolic and diastolic blood pressure and heart rate will be measured 3 times using an automated validated device. The repeat measurements will be made at 2-minute intervals and the lowest of the 3 measurements will be recorded on the eCRF, based on systolic BP. For all other visits, vital signs will be assessed once and recorded on the eCRF.

In case the cuff sizes available are not large enough for the patient's arm circumference, a sphygmomanometer with an appropriately sized cuff may be used. Orthostatic blood pressure will then be measured once with the patient in the standing position (after standing for 2 minutes). A sudden, significant fall in blood pressure (>20 mmHg) between 2 and 5 minutes after standing from the supine position will be interpreted as an orthostatic hypotension and will be documented in the patient chart and eCRF.

Patients will be carefully monitored after the first dose of study medication with a 6 hour post-dose monitoring period of hourly recording of orthostatic blood pressure.

Chest X-ray

To be performed only at screening of Part A and Part B. It is not required if performed within 60 days prior to randomization and if documentation is on file.

ECG

12-lead ECG to be performed after the patient has been resting quietly for at least 10-15 minutes.

Digital ECG devices will be provided to each clinical site by the central ECG laboratory for the duration of the study. The screening ECG report from the central reader must be available to confirm patient eligibility before randomization. A 12-lead ECG will be performed before and 6 hours after the first dose of study drug administration, while the patient is at the clinic.

Detailed instructions describing the process for recording and transmission of the digital ECGs will be outlined in the study-specific manual and provided to the site before the start of the study. Stand-alone ECGs will be obtained, printed, photocopied to preserve the ink if necessary, and kept at the site as source documentation.

ECG & Holter Monitoring

Dual function Digital ECG devices that are capable of capturing both stand-alone ECGs and Holter data will be provided to each clinical site by the central ECG laboratory for the duration of the study. Detailed instructions describing the process for recording and transmission of the digital ECGs and Holter data will be outlined in the study-specific manual and provided to the site before the start of the study.

Stand Alone/Static ECGs

Static ECGs will be captured at intervals as defined in the schedule of assessments (Section 9.1.1). The 12-lead ECG will be performed after the patient has been resting quietly in a supine position for at least 10-15 minutes. The screening 12-lead ECG report from a central reader must be available to confirm patient eligibility before randomization. 12-lead ECGs will be performed before and 6 hours after the first dose of study drug administration for all patients on Day 1 and for the first 75 patients at Day 5, while the patient is in the clinic. Six hour post dose ECG will be evaluated by treating neurologist, with input if needed from a local cardiologist or a central reader to confirm if extended monitoring is required. Simultaneously the ECGs will be printed out locally, photocopied to preserve the ink if necessary, and kept at the site as source documentation.

Each ECG tracing should be labeled with the study number, patient initials, patient number, date, and kept in the source documents at the study site. Only clinically significant abnormalities should be reported in the medical history/current medical conditions or adverse event CRF. Clinically significant findings must be discussed with the Medical Monitor before enrolling the patient in the study.

Continuous 12-lead Holter Monitoring

24 hour continuous cardiac monitoring (12 lead digital Holter monitoring) will be captured for all Part A patients at Day 1 and the first 75 patients at Day 5 and Day 8. Holter monitoring will start at least 15 minutes prior to dose and complete at least 24 hours post dose administration. Patient should be in the supine position prior to Holter application through the capture of the static pre-dose 12-lead ECG as well as for the acquisition of the 6 hour post dose 12-lead ECG. Holter analysis parameters will be described in the operations document.

Pulmonary Function Tests

Pulmonary function tests including FEV₁ and FVC measurements will be performed as scheduled [Table 1](#) and [Table 2](#) (Part A), and [Table 3](#) and [Table 4](#) (Part B). In addition, DLCO will be performed at screening and at the Week 24 visit of Part A and at Month 12 and Month 24 for Part B. With prior approval from the sponsor, DLCO will not be required at sites where there is no local DLCO testing facility available. In addition to scheduled assessments, the pulmonary function tests should also be performed as clinically indicated in the event of clinically significant pulmonary signs or symptoms. These tests will be performed at a high quality pulmonary function testing center with the appropriate certification (as locally required), and will be overseen by a pulmonologist who does not need to see the patients. If any PFT abnormalities occur, they will be followed until such time as resolution is confirmed or no further improvement is expected by the investigator (based on a follow-up period of not less than 3 months). Patients who discontinue due to respiratory AEs should be evaluated by a pulmonary specialist and further investigations (pulmonary function test, chest radiography, high resolution chest tomography or biopsy) should be performed as needed.

The technician should demonstrate the appropriate spirometry technique to the patient and follow the standard procedure. The quality of the tests must be accounted for including the technicians' comments (especially when, despite proper coaching of the patient, full collaboration cannot be achieved). A central trial statistician will calculate the FEV₁/FVC ratio.

A minimum of 3 acceptable maneuvers will be performed at each visit. The acceptability criteria are a satisfactory start of test and a satisfactory end of test. In addition, the technician should observe that the patient understood the instructions and performed the maneuver with a maximum inspiration, a good start, a smooth continuous exhalation, and maximal effort. The largest FVC and the largest FEV₁ will be recorded, after examining the data from all of the acceptable curves, even if the 2 values do not come from the same curve. Please refer to the American Thoracic Society/European Respiratory Society guidelines for standardization of spirometry and single breath determination of carbon monoxide uptake in the lung ([MacIntyre, 2005](#); [Miller, 2005a](#); [Miller, 2005b](#)).

If for any reason a patient is permanently discontinued from study medication the patient will have the pulmonary function tests performed at his last visit or within 30 days of the study drug discontinuation.

Two acceptable DLCO tests should be performed at each scheduled timepoint. A DLCO test is acceptable if it fulfills all the following criteria:

- Use of proper quality-controlled equipment
- Inspired volume of greater than 85% of largest vital capacity in less than 4 seconds

- A stable calculated breath hold for 10 (\pm 2) seconds. There should be no evidence of leaks or Valsalva or Mueller maneuvers
- Expiration in less than 4 seconds (and sample collection time less than 3 seconds), with appropriate clearance of dead space and proper sampling/analysis of alveolar gas.
- All values must be corrected for hemoglobin concentration in the study, using the central laboratory haemoglobin value for the respective visit.

Ophthalmological Examination

OCT will be performed as scheduled in [Table 1](#) and [Table 2](#) (Part A), and [Table 3](#) and [Table 4](#) (Part B). If there is a suspicion of macular edema, then general retinal exams including eye history, visual acuity, and dilated ophthalmoscopy will be obtained. A general ophthalmologist can do the examination, although a retinal specialist would be preferred to do the exams wherever possible.

Dermatological (Skin) Examination

Dermatological (skin) evaluations will be performed as part of the physical exam at screening, and then every 6 months in Part A and yearly in Part B, as scheduled in [Table 1](#) and [Table 2](#) (Part A), and [Table 3](#) and [Table 4](#) (Part B). Dermatological (skin) evaluations will be performed by the treating investigator or medically qualified designee. Patients with any suspicious finding noted during the examination will be referred to an appropriately qualified dermatologist for evaluation and treatment, if warranted.

Suicidality Assessment

Suicidality will be assessed using the C-SSRS ([Posner, 2011](#)) at all study visits during Part A and Part B. It will be self-administered through a validated IVRS.

Monitoring of AEs and SAEs

Throughout the course of the study, Part A (both periods) and Part B, every effort must be made to remain alert to possible AEs or SAEs. Refer to [Section 12](#) for definitions of AEs/SAEs, monitoring and reporting. Refer to [Section 12.4](#) for AEs of special interest.

Monitoring of Concomitant Therapy

The use of concomitant medication and procedures will be monitored throughout the study in Part A (both periods) and Part B. Refer to [Sections 9.5.7](#) and [9.5.8](#) for prohibited concomitant therapies.

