8.2.2. Safety (Secondary) Endpoints

Part A

Cardiac safety and tolerability during initial dose titration will be evaluated in Part A patients according to the following monitoring schedule:

- Day 1 (all Part A patients): Observation of patients predose and for the first 6 hours following initial dose administration; ECG predose and at Hour 6; continuous Holter monitoring for 15 minutes predose and for 24 hours following dose administration.
- Day 5 (first 75 patients): Observation of patients predose and for the first 6 hours following dose administration; ECG predose and at Hour 6; continuous Holter monitoring for 15 minutes predose and for 24 hours following dose administration.

- Day 8 (first 75 patients): Continuous Holter monitoring for 15 minutes pre-dose and for 24 hours following dose administration.

If clinically significant heart rate reduction or cardiac conduction abnormalities are not observed in the first 75 patients that are treated, Day 5 and Day 8 monitoring will be discontinued for the remaining patients enrolled in the study.

Part B

Monitoring during initial dosing for Part B will include:

Day 1 (all Part B patients): Observation of patients pre-dose and for the first 6 hours following initial dose administration; ECG pre-dose and at Hour 6

Monitoring during initial dosing for Part B may be modified based on safety and tolerability results observed during Part A, and will be implemented as needed in an amendment to this clinical study protocol.

Part A and Part B

Safety and tolerability will be evaluated in this study by the incidence and type of AEs, SAEs, AEs leading to discontinuation of study treatment, the incidence and type of laboratory abnormalities, vital sign, ECG, and physical exam abnormalities in all patients. In addition, descriptive characterization of target AEs of interest including bradycardia and heart conduction abnormalities (ECG, vital signs, continuous Holter monitoring [Part A only]), pulmonary toxicity (FEV₁, FVC measurements), and lung diffusion capacity testing [DLCO measurements), macular edema (optical coherence tomography [OCT]), hepatotoxicity (LFTs), cutaneous malignancy (dermatological exams), and suicidality (Columbia- Suicide Severity Rating Scale [C-SSRS]) will occur in both Part A and Part B of the study.

Safety assessments will include the following:

- AEs
- Laboratory evaluations
- Vital sign measurements
- ECG results
- Continuous Holter monitoring

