- MSFC practice. Three MSFC practice assessments must be performed before baseline: MSFC Practice 1 is to be performed at the screening visit, MSFC Practice 2 and MSFC Practice 3 may also be performed at the screening visit, or on other days between the screening and baseline visit).
- LCLA
- Pulmonary function tests including FEV₁ and FVC measurements, and DLCO
- OCT evaluation
- Dermatological examination.
- Suicidality assessment using the C-SSRS

- Record relevant prior and current therapy. A history of all prior medications needs to be documented to at least 4 weeks prior to study participation, and a history of previous treatments for MS needs to be documented for the prior 2 years
- SAEs to be recorded from the time of signing the informed consent; AEs to be recorded from the first dose of study drug.

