- c. Hepatotoxicity. Fingolimod caused frequent, reversible liver enzyme elevations greater than 3-fold above the upper limit of normal in up to 12% of patients; this was a significant cause of cessation of therapy. In this study, clinical chemistry analyses to assess LFTs will be performed. Every patient whose LFTs are abnormal will be followed until values return to baseline.
- d. Macular edema. Instances of serious macular edema were reported in fingolimod renal transplant studies, and a 0.8% incidence was reported as an SAE in fingolimod (1.25 mg dose) MS clinical studies. Nonclinical studies with RPC1063 have not revealed eye-related toxicities. In this study, measurement of central foveal thickness by OCT will be performed in all patients. For patients

with abnormal OCT findings or with visual signs or symptoms of macular edema, a general ophthalmologic examination including eye history, visual acuity, and dilated ophthalmoscopy will also be performed. Every patient whose ophthalmic evaluations reveal abnormalities will be followed until values return to baseline or no further improvement is expected by the investigator (based on a follow-up period of not less than 3 months).

Overall, the following procedures should be followed:

- Vital signs will be assessed in supine and standing position at every visit. A sudden, significant fall in blood pressure (> 20 mmHg) between 2 and 5 minutes after standing from the supine position will be interpreted as an orthostatic hypotension and will be documented in the patient chart and eCRF.
- Patients will be closely monitored in the clinic after their first dose of the initial dose titration regimen for a period of 6 hours after treatment. ECGs will occur predose and at Hour 6 following dosing, with more frequent assessments as clinically indicated; vital signs, including orthostatic blood pressure assessment, will be assessed predose and then hourly for 6 hours following dosing. See the monitoring guidelines in [Section 10.2.1.1](#) for further details.
- Clinicians should be particularly mindful of patients who have a low pulse at baseline (spontaneously or through drug induced β -receptor blockade), prior to administration of the study drug. Atropine IV is recommended as the first line treatment of bradycardia, up to a maximum daily dose of 3 mg. Furthermore, the common guidelines for treatment of bradycardia (e.g. Advanced Cardiac Life Support-ACLS guidelines) should be followed as appropriate:

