### 16.1.9 Documentation of Statistical Methods

Receptos, Inc.  
Protocol RPC01-201

Statistical Analysis Plan – Part A, V1.2  
Date Issued: May 20, 2014

The secondary safety endpoints of Part A are:

- AEs
- Laboratory evaluations
- Vital sign measurements
- ECG results
- Continuous Holter monitoring
- Physical and neurological examination
- OCT
- Pulmonary function tests
- Dermatological examination
- Columbia-Suicide Severity Rating Scale (C-SSRS)

The secondary PK and PD endpoints of Part A are:

- Standard PK parameters
- CBC with differential
- Plasma protein biomarkers (e.g., cytokines, chemokines, other inflammatory proteins)
- Total immunoglobulins (Igs) - IgA, IgG, IgM

Note: PK data from this study may be integrated with PK data from other clinical trials to further enhance a population PK analysis. Population PK analyses will be described under a separate analysis plan and documented in a separate pharmacometric report.

The exploratory endpoints of Part A are:

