**10.5 Pulmonary Function Testing**

The following laboratory tests will be included for pulmonary function testing (PFT) summary tables: forced expiratory volume in 1 second (FEV1), forced vital capacity (FVC), and diffusing capacity of the lung for carbon monoxide (DLCO). For FEV1 and FVC, summary tables for actual value, change, percent change, percent predicted, change in percent predicted, and percent change in percent predicted will be produced. For DLCO summary tables for actual value, change, and percent change will be produced. DLCO is collected at the local lab for each site, so results may be collected in domestic or SI units. DLCO results in domestic units (mL/min/mmHg) will be converted to SI units (mmol/min/kPa) prior to analysis using the following conversion factor:

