### 10.9 Other Assessments

A summary table of dermatological abnormalities by visit will be presented. Listings of dermatological abnormalities and abnormalities in optical coherence tomography (OCT) assessment will be provided.

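### OCT is a named Part A safety endpoint, but SAP 10.9 plans only a listing of abnormalities, so foveal thickness and OCT findings not reported as AEs get no summary by arm

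*Protocol*

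**What the plan says.** **Measurement.** Under Ophthalmological Examination, Protocol 11.2.1 says "OCT will be performed as scheduled in" Tables 1 and 2 for Part A. Those tables, with sections 10.1, 10.2.8 and 10.5, place OCT at screening, Week 24 and early termination. Protocol 12.4 specifies the quantity: "measurement of central foveal thickness by OCT will be performed in all patients".

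**Status.** Protocol 8.2.2 includes OCT in its list of safety assessments and names it as the tool for macular edema, one of the target AEs to be characterized descriptively. In SAP 4.2, OCT is an item under "The secondary safety endpoints of Part A are". The protocol synopsis also states that safety data will be both listed and summarized by treatment group. That sentence stands after the Part B methods but is worded for safety data in general.

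**Planned output.** SAP 10.9 says: "Listings of dermatological abnormalities and abnormalities in optical coherence tomography (OCT) assessment will be provided". No other part of the SAP plans an OCT output. The same section treats skin findings differently: "A summary table of dermatological abnormalities by visit will be presented".

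**The concern.** A named safety endpoint, measured before and after treatment in a randomized placebo-controlled comparison, would normally have a summary by arm. A listing of abnormal cases shows who was flagged. It does not show how many patients were examined, what percentage of each arm had a new abnormality, or how thickness moved from screening.

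Macular edema is an AE of special interest, and the protocol has study drug discontinued on a new or worsening diagnosis. Part B compares RPC1063 with interferon, so it cannot supply a contrast with placebo. If Part A does not summarize OCT by arm, that contrast is never presented for this endpoint.

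**Working it through.** The plan states no figure to reproduce here. The check is a comparison of planned outputs, followed by an illustration of scale.

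**1. Outputs for the measurements that Protocol 8.2.2 pairs with target AEs**

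| Target AE | Measurement | Output planned in the Part A SAP |
|---|---|---|
| Cardiac | Vital signs, ECG, Holter | Summary tables (10.3, 10.4); Holter heart rate in a separate plan (section 2) |
| Pulmonary | FEV1, FVC, DLCO | Tables of value, change and percent change (10.5); for example "For DLCO summary tables for actual value, change, and percent change will be produced" |
| Hepatic | LFTs | Multiples of ULN, overall and by visit, per arm (10.2.2) |
| Skin | Dermatological exam | Summary table by visit, plus listing (10.9) |
| Suicidality | C-SSRS | Summarized per arm (10.8) |
| Macular edema | OCT | Listing of abnormalities only (10.9) |

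The SAP defers Holter heart rate, population PK, the extension and Part B to separate plans (section 2), and PD analyses to a possible one (section 11). It names no separate plan for OCT.

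**2. What other tables already cover**

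SAP 10.1.7 tabulates macular edema as an AE of special interest. Protocol 12.7 has clinically significant changes in safety findings recorded as AEs, and these reach the AE tables. Two things remain without a summary: the thickness values, and OCT abnormalities that were not reported as AEs.

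**3. How much the AE count could show (illustration only)**

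Inputs: 70 patients per arm (SAP 5.1), so 140 on RPC1063. The only macular edema rate in the documents is 0.8%, for fingolimod 1.25 mg, reported as an SAE (Protocol 12.4).

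- Expected cases = n × p: 70 × 0.008 = 0.56 in one arm; 140 × 0.008 = 1.12 in both.
- Chance of no case = (1 − p)^n: 0.992^70 = 0.57; 0.992^140 = 0.325.

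At that rate the AE table would show no case in either RPC1063 arm about a third of the time.

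**4. Precision of a thickness summary (illustration only)**

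The 95% CI half-width for a two-arm difference in mean change is 1.96 × SD × √(2/n).

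- In SD units: n = 70 gives 0.33 SD; n = 59 gives 0.36 SD.
- With an SD of change of 8 to 15 micrometres (assumed; the documents give none): SD 8, n = 70 gives 2.65; SD 15, n = 60 gives 5.37.

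**5. What a mean can miss**

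Suppose one patient in an arm of 70 has a rise of 200 micrometres (assumed). The arm mean moves by 200 / 70 = 2.9 micrometres, about the smaller half-width in step 4. A mean alone could hide that patient, so the table must also show the largest increases.

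**The case against.** The strongest reply is that the protocol's promise concerns the adverse event, with OCT as the means of detecting it. Macular edema is tabulated, and clinically significant findings become AEs. Abnormalities left out of the tables are therefore mainly those the investigator judged not significant. SAP section 5 sorts listings by treatment group, so with about 70 patients per arm abnormal scans can be counted by hand. Physical examination is also a named secondary safety endpoint and is only listed (SAP 10.6). No safety hypothesis tests are planned. No passage promises an analysis of foveal thickness by arm. Part B has about 800 RPC1063 patients with OCT at Months 6, 12 and 24; at 0.8% that is 6.4 expected cases, and its SAP is a separate document.

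Much of this stands, and it limits the point to what section 2 of the working leaves over. A reader might infer that ophthalmic safety goes unanalysed in Part A. The documents do not support that, because of the AE tables. A reader might also infer that mean thickness change is the only ophthalmic quantity precise enough to be useful. That is not supported either: the SD is assumed, and nothing in the documents links mean change to rare focal edema.

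The reply does not supply the missing denominator or any summary of the measurement. A hand count from a listing of abnormal cases gives neither. Physical examination is not paired with a target AE in Protocol 8.2.2, whereas every other measurement that is paired gets a summary or a separate plan. Part B's larger numbers are against interferon, not placebo.

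**Conclusion.** The point holds in a limited form. For a named Part A secondary safety endpoint, the SAP plans a listing of abnormalities and no summary by arm. The OCT measurement, and OCT abnormalities not reported as AEs, have no count by arm, no denominator and no change from screening. This affects no efficacy conclusion and leaves the macular edema AE table intact. It is a cheap improvement to safety reporting.

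The conclusion rests on the comparison of outputs, not on the arithmetic. The 0.8% rate belongs to another drug and was reported as an SAE, and the SD range is an assumption; both only indicate scale. A reader might take the discontinuation rule for macular edema to be permanent. Protocol 12.4 uses that word for confirmed LFT elevations, not for macular edema, and the point does not depend on it.

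One matter cannot be settled from the documents: whether the eCRF records a numeric thickness or only normal/abnormal. The count of new abnormalities does not depend on this; the thickness summary does.

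**What to change.** In SAP 10.9, add one descriptive table by treatment group containing:

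- the number of patients examined, and the number and percent of them with a new OCT abnormality at Week 24 or early termination;
- where the eCRF captures a numeric value, central foveal thickness at screening and at Week 24 or early termination, with change from screening, using the worse eye per patient;
- the largest increases in each arm, for example the maximum, so that a single focal case is not hidden by the mean.

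Keep the listing and add no hypothesis test.

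The cost is one more table from assessments already scheduled, with no new visit or procedure. Protocol 13.3 allows the SAP to add analyses. The main drawback is that thickness may vary by device: the documents describe no OCT standardization or central reading, whereas Protocol 11.1.1 provides for both with MRI. A table footnote should say so.
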